11.6 Reporting of Adverse Events and Device Deficiencies

In the event of SAE, the PI will take the necessary actions and report it to the EC and the head of the institution. Additionally, the PI will inform the other PIs. For those reporting processes, Standard Operating Procedures will be followed.

All reportable AEs and device deficiencies, which will be collected in this study per Section 11.1 and 11.2, will be recorded in the subject's medical record, the study CRF, and promptly reported to Medtronic or its designee. PI/ Sub investigators are required to keep records on all relevant observations.

Reportable adverse events and device deficiencies will include the following information, at a minimum:

- Date of event
- Diagnosis and description of the event
- Assessment of the seriousness and relationship to the product(s) under investigation, therapy, and procedure, the disease under study and an underlying condition other than the disease under study (AE only)
- Model and identifier (serial, lot number) for the involved device (if applicable)
- Treatment (AE only)
- Outcome and date of resolution (AE only)

It is the responsibility of the PI or designated Sub investigator, to identify the occurrence of reportable AEs and DDs and to ensure the required information is accurately documented on the CRF.

11.6.1. Adverse Event and Device Deficiency Classification

Regulatory reporting of AEs and DDs will be completed according to local regulatory requirements. It is the responsibility of PI by any additional AE reporting requirements stipulated by the EC responsible for oversight of the study.

AEs will be classified according to the Table 3:

Table 3: Event Classification Responsibilities

What is Classified	Who Classifies	Classifications
Relatedness*	PI/ Sub investigator Medtronic	Relationship to the: 
• Procedure• Device• Therapy/Stimulation• Disease under study• An underlying condition other than the disease under study
Seriousness	PI/ Sub investigator	
• SAE• DD with SADE potential
	Medtronic	
• SAE• USAE• DD with SADE potential
Diagnosis	PI/ Sub investigator	Based on presenting signs and symptoms and other supporting data
	Medtronic	MedDRA term assigned based on the data provided by PI/ Sub investigator

*Adverse events that are classified as having a relationship of possible, probable or causal to the device, procedure or therapy/stimulation are considered to be related to the study device

11.7 Subject Death

The PI/ Sub investigator must notify Medtronic and the governing EC without unjustified delay after learning of a subject's death, regardless of whether the death is related to the device system or therapy. The PI/ Sub investigator should also attempt to determine, as conclusively as possible, whether such deaths are related to the device, procedure or therapy.

Any subject death will be reported on the Adverse Event and Study Exit CRF accordingly. For the Adverse Event eCRF, the death should not be reported as a diagnosis of the event, rather as an outcome of the event which led to death.

If an autopsy is conducted, a copy of the de-identified report will be provided to Medtronic. Medtronic

requests that all device system components that were being used at the time of the death be returned to Medtronic for analysis.

A copy of the death certificate, if available and allowed by state/local law, should be sent to the Medtronic clinical study team. When a death occurs in a hospital, a copy of the death summary report and all relevant hospital records, if available should be sent to the Medtronic clinical study team. When the death occurs at a remote study site, it is the investigative study site's responsibility to attempt retrieval of information about the death if a death certificate or summary report are unavailable. The PI/ Sub investigator creates summary of the death. Additionally, device disposition information should be updated, if available.

In summary, the following data will be collected:

- Date of death
- Detailed description of death
- Cause of death
- Relatedness to system and procedure
- Device interrogation information/reports (if available)
- Device disposition information (if available)
- Death summary/hospital records (if available and allowed by state/local law)
- Autopsy report (if available and allowed by state/local law)
- Death certificate (if available and allowed by state/local law)

11.8 Product Complaint Reporting

Product complaint reporting and vigilance reporting are applicable and DDs and AEs related to any market released device during the study must be reported. The reporting of product complaints except for all reportable AE information for this study is not part of the study and should be done in addition to the AE reporting requirements. Refer to local regulations for reporting requirements.

Product Complaint: Any written, electronic or oral communication that alleges deficiencies related to the identity, quality, durability, reliability, safety, effectiveness or performance of a medical device that has been placed on the market.

It is the responsibility of the PI/ Sub investigator to report all product complaint(s) associated with a

medical device distributed by Medtronic, regardless whether they are related to intended use, misuse or abuse of the product. Reporting must be done immediately and via the regular channels for market-released products. Medtronic will notify the Ras (e.g. CA) as applicable in accordance with the requirements upon learning of them and is not limited to AEs and DDs only.

12. Statistical Design and Methods

The study participants will be randomized to either sequence: the first treatment is aDBS and then cDBS, or the first treatment is cDBS then aDBS. According to the randomized sequence, the first treatment DBS mode is started in Period A and second DBS mode is started in Period B. Supporting analyses for the primary objective include verifying the lack of a period or carryover effect in randomized subjects.

The Early Adapter Part II study will be considered successful when the primary objective of the study is met. The main analysis of primary and secondary objectives will use the Complete Case set (CC) which include all subjects who initiate the aDBS treatment phase and have complete data for the respective analysis. The main analysis will include data from all sites. An assessment for poolability of the results across clinical sites will be conducted by descriptive analyses for individual sites for the primary and key secondary endpoint. Subject disposition will be reported in a CONSORT diagram to show the flow of participants through stages of the study.

12.1 General Aspects of Analysis

Data analysis will be performed by Medtronic-employed statisticians or designees. All statistical analyses will be performed using Statistical Analysis System (SAS) for Windows (version 9.4 or higher, SAS Institute Inc. Cary, NC), R (version 3.2 or higher, R Foundation for Statistical Computing, Vienna, Austria) or any validated statistical software.

In the primary analysis report, continuous data will be summarized using standard descriptive statistics including the mean, standard deviation, median and range or interquartile range. Categorical variables will be summarized using frequency counts and percentages. For events that can occur more than once in a single subject, such as adverse events, the percentage will be based on subjects experiencing the event; both subject and event counts will be reported. P-values will be two-sided, with values less than 0.05 indicating statistical significance.

Since the impact of missing data is expected to be small no multiple imputation method for missing data is planned.

The Gatekeeping procedures will be applied for the multiple testing procedures. After the primary study objective is met ($\alpha=0.05$, two-sided gatekeeper), the secondary study objective will be carried out at $\alpha=0.05$ two-sided. No multiplicity adjustment will be performed for evaluations of the additional study objectives. No imputation will be used.

The analyses will use two population sets:

- The Complete Case set (CC) analysis includes all patients enrolled in the study those sign Patient Informed Consent, fulfill the inclusion and exclusion criteria and randomized who initiate the aDBS treatment phase and have complete data for the respective analysis. The CC set will be used for primary and secondary objectives.
- The As-Treated Set (AT) includes subjects who are treated with continuous Deep Brain Stimulation (cDBS) and/or adaptive Deep Brain Stimulation (aDBS) at enrollment and/or the aDBS treatment phase and uses the observed treatment used for each subject in each phase. This set will be used for safety assessment.

12.2 Analysis Execution

Formal analysis for the Early Adapter II trial will occur when all active subjects have completed the aDBS treatment Phase of the study. Analysis will include both the primary and secondary objectives. Additional objectives will be addressed based on available data. A final report will be prepared once all data collection has ended and all subjects have completed the study or have been exited. The inferential analysis for the primary and secondary objectives will not be updated for the final report.

Additional details of the analyses outlined in this section and additional exploratory analyses will be described in detail in the statistical analysis plan prior to the data freeze for the primary analysis report. All results will be reported in the final study report. Any departure or deviation from these planned statistical methodologies will be documented and discussed in the Statistical Analysis Plan that will include the statistical rationale for divergence. If there are any changes from the original statistical analysis plan, revise the CIP or statistical analysis plan and describe the changes and their analysis results in the final study report.

12.3 Interim Analysis

No interim analyses are planned for this study.

12.4 Primary Objective

The primary objective is to demonstrate decreased Total Electrical Energy Delivered (TEED) during adaptive (aDBS) as compared to continuous DBS (cDBS). For this endpoint the CC cohort will be used.

The endpoint is the energy use as measured by TEED during the aDBS as compared with TEED during the cDBS during the aDBS treatment phase (from period A to period B). Denote the TEED on aDBS by $TEED_{aDBS}$ and the corresponding value for cDBS by $TEED_{cDBS}$. For each patient the difference between $TEED_{aDBS}$ and $TEED_{cDBS}$ will be calculated ($TEED_{aDBS} - TEED_{cDBS} = TEED_{DIFF}$). The hypothesis that $TEED_{DIFF} \neq 0$

will be tested by means of the Student's paired t-test and a p-value less than, or equal to, 0.025 will be regarded statistically significant. The formal hypothesis testing is:

$$H_0: \mu_{\text{TEEDaDBS}} - \mu_{\text{TEEDcDBS}} = 0$$

$$H_a: \mu_{\text{TEEDaDBS}} - \mu_{\text{TEEDcDBS}} \neq 0$$

Where the difference ($\mu_{\text{TEEDaDBS}} - \mu_{\text{TEEDcDBS}}$) is the electrical energy saving.

TEED is defined as the total energy delivered by an electrical system through the DBS leads over an arbitrary period of time. TEED is determined by the stimulation parameters (e.g., pulse width, frequency, amplitude) and the measured impedance.

The calculation of TEED when using constant voltage is:

$$\text{TEED} = (\text{Voltage}^2 * \text{Frequency} * \text{Pulse width}) / \text{Impedance}$$

The calculation of TEED when using constant current is:

$$\text{TEED} = \text{Current}^2 * \text{Frequency} * \text{Pulse width} * \text{Impedance}$$

The previous formulas can be used without modification with legacy lead.

When the lead is a directional lead with separate electrodes and it is programmed in Directional Stim Mode or Ring Mode Stimulation, each contact is considered independent. For each segment that is activated, TEED will be calculated individually using the formulas above, and then summed to obtain the total TEED for the lead. Leads programmed with monopolar settings will use the electrode unipolar impedance between the case and the active electrode. If 2 cathodes are used (dual monopolar settings), TEED will be calculated for each contact separately, and total TEED will be determined for the lead as the sum of the two TEED. Leads programmed to bipolar will use the impedance between the active electrodes.

Directional Stim Mode may be programmed during the follow-up phase. The primary endpoint on the difference in TEED will be assessed by means paired t-test to compare the difference in TEED for aDBS (preferred mode, single or dual threshold) to cDBS. Normality of the outcome will be assessed with the Shapiro-Wilk test. If large violations to the normality assumption are observed ($p < 0.05$), the primary analysis will use a Wilcoxon signed-rank test to assess statistical significance.

To compute TEED using the formula above, the average current drain from the JSON session data will be computed using the average stimulation currents from the timeline feature in the 14 days prior to the visit. This will be computed as the average of the currents from the timeline feature using the epochs that align with the analysis set (e.g., As-Treated analysis set uses the actual aDBS mode as reported from the device). The pulse-width, frequency, and impedance will be determined from the JSON session data as per study procedure.

12.4.1. Supporting analyses

The analysis approach makes two main assumptions: no period effect and no carryover effect (including their interaction). These assumptions will be tested first. If the period and carryover effects is not significant (i.e. the p-value is greater than or equal to 0.10), then the data from the two periods can be combined and analyzed. Otherwise, the data only from period A can be used to estimate the treatment effect. Details on supporting analyses will be reported in the statistical analysis plan.

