12.8 Target Sample Size and Justification

Target sample size: 20-30 subjects

[Rationale for the sample size]

Based on the registry data and the bench testing, a conservative estimate based on the first quartile of TEED data for initial devices in the registry, TEED is expected to decrease between 35 and 22 units for aDBS single threshold mode and aDBS dual threshold mode, respectively^{56,57}. Due to the expected 5% of single threshold with bilateral aDBS with an expected TEED difference of 35 units, 25% of subjects in single threshold but with unilateral aDBS with an expected TEED difference of 18 units and 70% in dual threshold with an expected TEED difference of 22 units, we assume a difference of 22 units defined as the weighted average of those differences. A SD of 28 results in a medium to large effect size of 0.79⁵⁸. Based on these assumptions, the sample size was estimated using a two-sided (alpha=0.05) paired T-Test means (PASS 2019) to compare the difference in aDBS TEED to cDBS TEED of 22 and a standard deviation of 28, a minimum of 20 subjects achieves at least 90% power for the detection of an effect size of 0.79.

it is estimated that between 20-30 subjects implanted with a commercially available Medtronic DBS system with Percept PC INS will be enrolled to obtain a study population of 20 subjects who complete the aDBS treatment phase. .

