7.9.1.5 Supporting analyses

In order to demonstrate the decreased TEED during adaptive (aDBS) as compared to continuous DBS (cDBS), using a within-subject comparison in this crossover design, it is necessary to test for period effects (where the treatment effect is dependent upon which treatment was applied first) and carryover effects (where the treatment effect from the first crossover period affects the response during the second period). The average TEED will be analyzed using a general linear model appropriate for a two-treatment, two-period crossover design to inspect the period effect and carry-over effect. A significance level of 0.15 will be applied to the analysis of period effect and carry-over effect to allow for a more conservative analysis. Should any significant period or carryover effects be detected, data from the first crossover period may be compared between randomized groups in a parallel-design fashion.

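### The period/carryover pretest (0.10 in the protocol, 0.15 in the SAP) is not barred from replacing the two-period primary analysis; if it does, error exceeds its nominal level and power falls below 90%

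*Protocol*

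**What the plan says.** Protocol 12.4.1 says of the no-period and no-carryover assumptions: "These assumptions will be tested first". The two periods may be pooled if the effects are not significant ("i.e. the p-value is greater than or equal to 0.10"). If they are, "Otherwise, the data only from period A can be used to estimate the treatment effect".

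SAP 7.9.1.5 has the same structure at another level: "A significance level of 0.15 will be applied to the analysis of period effect and carry-over effect". It calls this level the more conservative choice. If any significant period or carryover effect is found, "data from the first crossover period may be compared between randomized groups in a parallel-design fashion".

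The primary test itself is stated without reference to this pretest. Protocol 12.4 and SAP 7.9.1.4 give a paired t-test of TEED (total electrical energy delivered) on aDBS against cDBS, with a Wilcoxon signed-rank test if normality fails. The sample size rests on that paired test alone (Protocol 12.8, SAP 6). No power is given for a Period A comparison.

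**The concern.** Read in order, Protocol 12.4.1 makes pooling conditional on passing a pretest. Four things follow.

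- **The decisive analysis is open.** The protocol says Period A data can be used and the SAP says they may be compared. Neither says whether that result replaces the paired test or stands beside it. Study success rests on the primary objective (Protocol 12), which also gates the secondary objective (Protocol 12.5).
- **A two-stage rule does not hold its error rate.** The carryover test and the Period A comparison share the Period A data. A chance imbalance that makes carryover look significant also tends to make the Period A comparison significant.
- **A period effect is no reason to drop Period B.** A period term in the crossover model removes it. The SAP also defines a period effect as the treatment effect depending on which treatment came first. That is carryover or treatment-by-period interaction, so the trigger is mis-specified.
- **The thresholds conflict.** A pretest p-value between 0.10 and 0.15 leads to pooling under the protocol and to the fallback under the SAP.

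Carryover is also limited by design. TEED uses the 14 days before a visit that falls 45 (±7) days after the mode change, so the window opens about 45 − 14 = 31 days into the new mode, or 38 − 14 = 24 days at the shortest.

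**Working it through.** **1. The plan's own figure.** Protocol 12.8 sizes the trial for a paired t-test at two-sided 0.05. Its inputs: "to compare the difference in aDBS TEED to cDBS TEED of 22 and a standard deviation of 28". The claim is 90% power or more with 20 subjects.

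- Noncentrality = (22/28) × √20 = 0.786 × 4.472 = 3.51.
- Paired t-test, 19 df: power 0.915. The smallest n for 90% is 20, so the claim reproduces.
- SAP inputs (28 and 36) give 0.910.
- With a period term, 18 df: 0.913 (protocol inputs) and 0.908 (SAP inputs).

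**2. Chance of triggering with no true effect.** For normal data and balanced sequences the period test (within-subject differences) and the carryover test (subject sums) are independent, so the chance that either fires is:

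- at 0.10: 1 − 0.90² = 19.0%
- at 0.15: 1 − 0.85² = 27.75%, about 28%

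**3. Power of the fallback alone.** The SD of the paired difference is 28, so the per-period SD is 28/√(2(1 − ρ)), where ρ is the within-subject correlation. The documents do not give ρ; 0 to 0.9 is an assumed range. Ten against ten assumes 20 completers and 1:1 sequences; Protocol 9.7 names permuted blocks but no ratio.

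| ρ | Per-period SD | Period A power, 10 vs 10 |
|---|---|---|
| 0 | 19.8 | 0.65 |
| 0.5 | 28.0 | 0.38 |
| 0.9 | 62.6 | 0.12 |

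**4. The two-stage rule.** Simulated with at least 100,000 trials per setting, normal data, protocol inputs, two-sided 0.05 and no true period or carryover effect. If either pretest is significant, an unpaired t-test on Period A is used; otherwise the paired t-test.

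| Pretest level | Type I error, ρ = 0 / 0.5 / 0.9 | Power, ρ = 0 / 0.5 / 0.9 |
|---|---|---|
| none | 0.050 at each | 0.915 at each |
| 0.10 | 0.067 / 0.079 / 0.088 | 0.86 / 0.82 / 0.80 |
| 0.15 | 0.069 / 0.079 / 0.087 | 0.84 / 0.78 / 0.74 |

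The source of the inflation is visible under the null: after a significant carryover test at 0.10, the Period A comparison rejects in about 24-48% of trials.

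**5. Other readings of the plan.**

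- Only carryover triggers the switch: power about 87-88% (0.10) or 85-87% (0.15), type I error about 7-9%.
- Protocol 12.4 threshold of 0.025 with the 0.10 pretest: type I error about 3.5-4.5%, power about 73-79%, against 85% with no pretest.
- SAP inputs 28 and 36, 0.15 pretest, one-sided 0.05: type I error about 6.6-8.4%, power about 78-89%.

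**6. A real period shift, no carryover.** With an assumed shift of 15 units and ρ from 0.5 to 0.9, the rule fires in about 77% (0.10) or 84% (0.15) of trials. Power falls to about 30-51% or 25-47%. A period-adjusted crossover contrast keeps 91%.

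**The case against.** The strongest objection is that the plan never says the Period A result becomes the primary result. Both passages sit under a supporting-analyses heading, the wording is permissive, and the primary test is stated without this condition. SAP section 8 also describes the main analysis of the primary objective as excluding sensitivity and supporting analyses. If Period A is only a side estimate, the primary test keeps its 5% error and 91.5% power. This stands, and it makes every figure above conditional. A reader might infer that the plan commits to discarding Period B, or that its error rate is already inflated; the documents do not establish either. But they do not exclude the switch, and testing first and then writing 'otherwise' points towards a gate.

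Further objections stand in part:

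- **Threshold.** At the 0.025 of Protocol 12.4 the two-stage error stays below 5%. It still exceeds 0.025, and power still falls.
- **Trigger.** The protocol's grammar leaves unclear whether a period effect alone triggers the switch. The SAP's reference to any significant period or carryover effect favours that reading, and the carryover-only reading still misses 90%.
- **Period shift.** The 15-unit shift has no source and exceeds half the SD, while the plan requires stable cDBS settings and medication. A 3-unit shift triggers the rule in only 22-32% of trials. Step 6 shows the mechanism and is not a forecast.
- **0.10 against 0.15.** The protocol leaves details to the SAP, and the SAP offers a reason. The reason does not hold: the higher level fires more often and costs more power.

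**Conclusion.** The concern holds in conditional form. The documents leave open whether a pretest can replace the two-period primary analysis, set it at two different levels, and allow the choice after the data are seen. If the switch decides the result, the stated power of at least 90% is not met in any setting examined, and type I error exceeds its nominal level in every setting without a true period shift. At two-sided 0.05 with either trigger, error is about 6.5-9%, and power is about 80-86% (0.10) or 74-84% (0.15).

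The size depends on the undocumented correlation, the assumed 1:1 split with 20 completers, the trigger reading and the significance threshold. The direction does not change across the readings examined. Separately from the arithmetic, a period effect alone does not justify dropping Period B, and the SAP's definition of a period effect is wrong.

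**What to change.** In Protocol 12.4.1 and SAP 7.9.1.5:

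1. Delete the pretest as a gate, which also removes the 0.10/0.15 conflict.
2. State that the within-subject two-period comparison of TEED on the planned Complete Case set, with a period term, is always the primary analysis.
3. Report period and carryover estimates with confidence intervals, descriptively.
4. Label any Period A comparison as a sensitivity analysis that never replaces the primary.
5. Correct the SAP's definition of a period effect to a difference between periods common to both treatments.

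A new analysis set or a mixed model is not needed. The Wilcoxon fallback for non-normal data can stay if it also uses both periods; the SAP should say how it handles the period effect.

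The cost is wording in two documents and one degree of freedom: power 91.3% instead of 91.5% on the protocol's inputs. The primary significance threshold (0.025 in Protocol 12.4, 0.05 in Protocol 12.1 and SAP 7.9.1.2) should be reconciled in the same amendment, because the error rate of any rule is judged against it.
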